14.1 Adverse Events

All AE verbatim terms reported on the eCRFs will be coded using the Medical Dictionary for Regulatory Activities (MedDRA® version 24.1).

All reported AEs (including non-TEAEs) will be listed. Separate listings will be provided for SAEs, TEAEs leading to study drug discontinuation, DLTs, AESIs, SUSARS, AEs related to adrenal insufficiency, and AEs related to COVID-19.

For all TEAE tables, counting will be by subject and not by event. Additionally, if a subject reported the same TEAE on multiple occasions, the highest severity (severe > moderate > mild) or study drug relationship (related > probable > possible > unlikely > unrelated) recorded for the event will be summarized. All TEAE summary tables will present the number and percentages of subjects reporting TEAEs, unless otherwise specified. A summary of TEAEs by severity, seriousness, and relation to study drug will be tabulated.

An overall summary of TEAEs will be presented. The overall summary will include the number and percentage of subjects experiencing any AEs, TEAEs, study drug related TEAEs, TEAEs by maximum severity (highest toxicity grade), SAEs, study drug related SAEs, DLTs, SUSARs, TEAEs of adrenal insufficiency, TEAEs leading to study drug discontinuation, and deaths.

The number and percentage of subjects experiencing each TEAE, study drug related TEAE, and SAEs will be summarized by treatment group according to system organ class and preferred term. An additional table including only preferred term summarized by treatment for the number and percentage of subjects experiencing each TEAE will be presented as well.

14.2 Clinical Laboratory Evaluation

Laboratory parameters hematology, chemistry, coagulation, lipid panel, thyroid panel, and other tests will be summarized by treatment and scheduled time point from randomization, based on actual treatment received at each scheduled time point and will include both observed values and change from baseline values. Subject-level listings will be provided for urinalysis and all the

aforementioned laboratory parameters. In addition, subjects meeting the following Hy's law criteria will be identified and listed:

- Alanine aminotransferase (ALT) $> 3 \times \text{ULN}$
- Aspartate aminotransferase (AST) $> 3 \times \text{ULN}$
- Total bilirubin (TBL) $> 2 \times \text{ULN}$

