6.1.6. Adrenal Insufficiency Stopping Criteria

Symptoms of adrenal insufficiency include weakness, tiredness, anorexia, nausea, vomiting, abdominal pain, orthostasis and muscle and joint aches. Weight loss and hypotension (eg, systolic blood pressure <110 mmHg) are also associated with adrenal insufficiency. Hyponatremia, hyperkalemia, hypercalcemia, azotemia, anemia, and eosinophilia may accompany adrenal insufficiency. It is important to note that many of these signs, symptoms and laboratory findings are nonspecific and commonly occur in persons without adrenal

insufficiency. The Investigator should use their clinical judgment when determining whether the signs, symptoms or laboratory findings are isolated AEs or are possibly due to adrenal insufficiency.

The Investigator is strongly encouraged to contact the medical monitor to review the presentation and discuss the plan for subjects with any AEs of adrenal insufficiency or cortisol measurements below the normal range.

If a subject develops clinical and/or laboratory findings of adrenal insufficiency that are confirmed with serum cortisol measurement, the AE of "adrenal insufficiency" should be reported on the AE/SAE CRF. The sign(s), symptom(s) and laboratory findings resulting in the diagnosis of adrenal insufficiency will be collected on separate Adrenal Insufficiency CRF and should not be individually recorded on the AE CRF. If the serum cortisol level is within the normal range, the individual symptoms and/or other laboratory findings should be reported as individual AEs.

In the absence of clinical or laboratory findings of adrenal insufficiency, unconfirmed serum cortisol levels below the normal range should not be reported as AE. Confirmed by repeat serum cortisol levels below the normal range, even in the absence of clinical or laboratory findings of adrenal insufficiency, are to be reported as an AE of adrenal insufficiency.

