8.3.5.3. Clinical Laboratory Data

Clinical laboratory test results will be listed by subject. Reference ranges provided by the laboratory for each parameter will be used to evaluate the clinical significance of laboratory test results. Values outside the relevant reference range will be flagged in the listings. Abnormal clinical laboratory test results will be listed in a separate listing.

Laboratory data will be summarized in terms of observed values, changes from baseline, values relative to normal ranges, and changes from baseline relative to normal ranges.

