4 PURPOSE OF THE ANALYSIS PLAN

This statistical analysis plan (SAP) pre-specifies the statistical analysis methods for supporting the completion of topline results and an abbreviated clinical study report (CSR) of Study SPR001-210 for tildacerfont, an investigational drug candidate designed to treat polycystic ovary syndrome (PCOS). This SAP will be used to analyze the safety and efficacy data collected during the study. Dose-exposure-response analyses combining data across multiple studies will be conducted using a separate pharmacokinetics SAP. The planned analyses identified in this SAP may be included in regulatory submissions and/or future manuscripts.

The analysis methods described in this plan are considered *a priori*, in that they have been defined prior to clinical database freeze and treatment un-blinding. Exploratory analyses that are not defined in this SAP may be performed to support the clinical development program. Any post-hoc or unplanned analyses that are performed for the CSR, but not defined in this SAP, will be documented in the CSR. Changes from the planned analyses stated in the study protocol are described in [Section 15](#). Should the SAP and the protocol be inconsistent with respect to any further planned analyses, the language of the SAP is governing.

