5.2.3.5 Clinical Laboratory and Urinalysis

Clinical laboratory assessments include serum chemistry, hematology, coagulation, lipid panel, thyroid panel, cortisol, and urinalysis. eGFR will be calculated from blood creatinine measured as part of screening clinical chemistry. Clinical lab assessments will be performed at Screening, Day 1, Week 4, Week 8, and Week 12.

Clinically significant adverse findings from laboratory or urinalysis assessments will be recorded on the AE CRF.

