9.1 Presentation of Summary Statistics

For most summary statistics, data will be analyzed and displayed in tabular format.

Unless otherwise specified, continuous efficacy hormones ([Section 5.2.2.1](#)) will be summarized using a 11-point descriptive statistics (i.e., n, mean, standard deviation [SD], median, 25% quartile [Q1], 75% quartile [Q3], minimum, maximum, geometric mean, geometric coefficient of variance [CV%], 95% confidence interval [CI] for geometric mean [including geometric mean ratio and its 95% CI]).

All other continuous variables will be summarized using an 8-point descriptive summary (n, mean, SD, median, Q1, Q3, minimum, and maximum) unless otherwise specified.

The same number of decimal places as in the observed value will be presented when reporting minimum and maximum; 1 additional decimal place than in the observed value will be presented when reporting mean, median, Q1, Q3, geometric mean, 95% CI; 2 additional decimal places than in the observed value will be presented when reporting SD. Geometric CV% will be reported to one decimal place.

All categorical/qualitative data will be presented using the frequency of events and percentages. All percentages will be presented to 1 decimal place, unless otherwise specified. Percentages equal to 100 will be presented as 100% and percentages will not be presented for zero frequencies, with the exception of binary variables. For summaries of AEs and concomitant medications (CMs), the percentages will be based on the number of subjects who received study drug.

All analyses and summaries will be produced using SAS® version 9.4.

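### SAP 14.2 omits, without declaring it, the normal-range and shift summaries planned in Protocol 8.3.5.3, so out-of-range laboratory values that never become adverse events, including unconfirmed asymptomatic low cortisol, are counted in no by-arm table

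*SAP*

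**What the plan says.** Protocol 8.3.5.3 lists four laboratory summaries. The first two are observed values and changes from baseline. The last two are "values relative to normal ranges, and changes from baseline relative to normal ranges". On listings it adds "Values outside the relevant reference range will be flagged in the listings" and asks for abnormal results to be listed separately.

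SAP 14.2 summarizes hematology, chemistry, coagulation, lipid panel, thyroid panel and a residual group of other tests by treatment and scheduled time point "and will include both observed values and change from baseline values". It then provides subject-level listings and states that "subjects meeting the following Hy's law criteria will be identified and listed". It mentions no range categories, shift tables, out-of-range flags or abnormal-results listing.

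SAP 5.2.3.5 treats cortisol as a safety test in its own right: "Clinical laboratory assessments include serum chemistry, hematology, coagulation, lipid panel, thyroid panel, cortisol, and urinalysis". SAP 14.2 does not name it.

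On precedence, SAP Section 4 states: "Should the SAP and the protocol be inconsistent with respect to any further planned analyses, the language of the SAP is governing". The same section says that changes from the protocol's analyses are described in Section 15. That section covers the exploratory efficacy analyses, the MMRM and the added responder thresholds, and nothing on laboratory data.

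**The concern.** Laboratory safety signals in a small trial tend to appear as a few individuals crossing a limit. Counts outside range and baseline-to-post-baseline shifts are the tables that show this by arm, and they are the two summaries missing from the SAP. Tildacerfont acts on the adrenal axis, and a cortisol below the normal range starts the evaluation pathway in Protocol 6.1.6. The number of subjects in each arm who fell below range is therefore something a reader of the study report would look for. If the tables follow SAP 14.2 as written, that number would have to be assembled by hand from listings that are no longer required to carry flags. A safety summary promised in the protocol would be lost with no recorded decision to drop it.

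**Working it through.** No figure in the plan is at issue, so the check is a side-by-side reading.

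| Item | Protocol 8.3.5.3 | SAP 14.2 |
|---|---|---|
| Observed values | yes | yes |
| Change from baseline | yes | yes |
| Values relative to normal range | yes | not specified |
| Changes relative to normal range | yes | not specified |
| Out-of-range flags in listings | yes | not specified |
| Separate listing of abnormal results | yes | not specified |
| Hy's law listing | not in this section | yes |

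**Is the difference declared?** Protocol 8.3.1 requires changes to its analyses to be pre-specified in the SAP. SAP Section 15 is the place for this and has no laboratory entry.

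**Where does cortisol fall in 14.2?** Protocol 7.1.5 places it within clinical chemistry. Protocol 12.4 and SAP Table 8 place it in the hormone panel, which 14.2 does not list. It is therefore covered under chemistry or under other tests, depending on which text the programmer follows.

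**Which low cortisol values reach a by-arm table?** Following Protocol 6.1.6 into SAP 14 and 14.1:

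1. Low cortisol with clinical or laboratory findings is an adverse event of adrenal insufficiency. It is counted in the overall TEAE summary, by treatment group and dose level.
2. "Confirmed by repeat serum cortisol levels below the normal range" are also reported as adrenal insufficiency, even with no findings. They are counted in the same place.
3. A low value without findings that is not confirmed on repeat is not reported as an adverse event, so it is not counted there. Under SAP 14.2 it appears only in a subject listing and possibly as the minimum for its arm and visit.

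**Can case 3 arise at the highest dose?** The only scheduled cortisol during 200 mg dosing is at Week 12. Drug is dispensed at Day 1, Week 4 and Week 8 and returned at Week 12 (Protocol 5.1 and 5.5). My inference is that a repeat prompted by a low Week 12 value would probably be drawn after dosing has ended. If that repeat is normal, the on-drug low value stays unconfirmed and is counted nowhere.

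**Other tests.** Protocol 7.2.1 makes an abnormal result an adverse event only under stated conditions, and repeating the test is not one of them. Results that meet none of those conditions fall into the same gap.

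**What does the 8-point summary recover?** SAP 9.1 gives n, mean, SD, median, quartiles, minimum and maximum. The minimum shows that at least one subject was low, but not how many. With the planned 26 tildacerfont subjects, all with a value at the visit, the first quartile sits at rank 0.25 × 26 = 6.5, in practice the seventh ordered value. So anything from 1 of 26 (3.8%) to 6 of 26 (23.1%) below range would leave the minimum below the limit and the first quartile within it. This describes what the table can show and is not a prediction. The actual arms will be smaller, because Section 15 records early discontinuation.

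**The case against.** The strongest reply is that the important cases are already counted. Protocol 6.1.6 requires a repeat 8 A.M. cortisol after a low routine value, and confirmed lows become adrenal insufficiency events even without symptoms. SAP 14.1 tabulates those events and the TEAEs leading to discontinuation, and lists adrenal-insufficiency events separately. Liver values meeting stopping criteria are reported as events of special interest. This stands. A reader might infer that low cortisol would appear in no table by arm; the documents do not support that.

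Second, a reader might infer that the SAP keeps only means and changes. It does not. The 8-point summary includes quartiles and extremes, although it gives no count of subjects.

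Third, 14.2 says what the summaries will include, not that they include nothing else, and SAP Section 9 leaves presentation conventions to mock shells that are not part of these documents. The shells may hold the missing tables. This is possible, but it does not settle the point: the shells are described as covering conventions, and a protocol-specified summary should be visible in the SAP or its removal declared.

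Fourth, with few subjects the listings can be read directly. That is partly true, but 14.2 no longer requires flags or an abnormal-results listing. The SAP does not rely on listings alone for ECGs: Section 14.4 gives numbers and percentages outside thresholds by treatment and time point, together with flagged listings.

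**Conclusion.** The point holds in a limited form. SAP 14.2 leaves out two of the four laboratory summaries in Protocol 8.3.5.3, as well as the flags and the abnormal-results listing, and Section 15 is silent. The consequence is confined to values that never become adverse events: unconfirmed asymptomatic low cortisol, probably including some Week 12 values on 200 mg, and other out-of-range results below the reporting threshold. How many subjects that would be cannot be derived from the documents.

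It would go too far to conclude that the safety objective would not be met. The protocol's safety endpoint is adverse events and serious adverse events, which SAP 14.1 tabulates.

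The conclusion assumes that the tables follow the text of 14.2 and that the mock shells do not add the missing summaries. The Week 12 argument also assumes that a repeat sample comes after the last dose. The change should be made, because a planned safety summary is otherwise lost and restoring it is easy.

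**What to change.** In SAP 14.2:

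- Add n (%) below, within and above the laboratory's normal range, by arm, dose level and visit.
- Add shift tables from baseline to each visit and from baseline to the worst on-treatment value, by arm and dose level. State whether worst means lowest or highest for each test.
- Name cortisol explicitly. Add n (%) of subjects with any on-treatment cortisol below the normal range, whether or not confirmed. Include unscheduled samples, and define on-treatment so that the Week 12 sample counts.
- Restore the out-of-range flags and the separate listing of abnormal results.

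If the sponsor prefers not to produce these tables, the omission should be declared and justified in Section 15.

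The cost is a short SAP edit and a few standard tables from data already collected. No clinical rule or study procedure changes.

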14.3 Vital Signs

Descriptive statistics for pulse rate, respiratory rate, temperature, including baseline values and change from baseline values, will be summarized by treatment group and scheduled time point. All vital signs parameters will be listed.

14.4 12-Lead Electrocardiogram

Electrocardiogram (ECG) data, such as clinical interpretation of ECGs, heart rate (HR) values, and interval assessments of RR, PR, QRS duration, QT interval, and the Fridericia's corrected value of the interval between the Q and T waves on the ECG tracing (QTcF) will be listed.

Descriptive statistics for observed values and change from baseline at each scheduled time point will be presented for these 12-lead ECG interval and HR assessments.

In addition, the number and percentage of subjects with any abnormal values (i.e., outside a pre-specified threshold) will be summarized by treatment and scheduled time point. The pre-specified levels of ECG thresholds are provided by Spruce (See [Table 5](#) below).

Table 5 Pre-Specified Threshold Levels for ECG Parameters

ECG Parameter	Pre-Specified Level
Heart Rate (bpm)	$< 40, > 120, > 130$
Heart Rate Change from Baseline (bpm)	$> 20, > 30$
QRS Interval (msec)	> 120
QTcF (msec)	Normal: ≤ 450 Borderline: > 450 to 470 Prolonged: > 470 $> 450, > 500$
QTcF change from Baseline (msec)	$\leq 30, > 30$ to $60, > 60$

All ECG parameters will be listed with flags for the above pre-specified level. A separate listing of subjects with values of QTcF > 500 msec or an increase > 60 msec will be provided, as necessary.

14.5 Psychiatric Evaluations

All responses from the Baseline/Screening Version of the Columbia–Suicide Severity Rating Scale (C-SSRS) assess both lifetime history and history from the last 6 months will be listed by subject and by visit. Tables will include results from the Suicidal Ideation and Suicidal Behavior sections of the C-SSRS. Number and percentage of subjects with a response of “Yes” at any point on the Suicidal Ideation and Suicidal Behavior items will be summarized by treatment group and scheduled time point, if sufficient number (i.e., > 5 in any dose level) of subjects responded “Yes”.

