6.1.9. Study Stopping Criteria

If any of the following criteria are met, the study will be stopped.

1. If 3 or more subjects on active drug experience a drug-related AESI
2. If 1 or more subjects on active drug experience a drug-related TEAE that is serious (TESAE) and results in death (Grade 5)
3. Any other safety trend or finding that creates an unacceptable risk-benefit profile for subjects participating in the study

Intensity should be evaluated per definitions in [Section 7.2.3.1](#). Seriousness criteria are provided in [Section 7.2.2](#). An unblinded Medical Monitor separate from the study team will monitor if study stopping criteria are met.

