7.1.6. Psychiatric Evaluations

7.1.6.1. Columbia-Suicide Severity Rating Scale (C-SSRS)

The C-SSRS will be used during the study to monitor suicidal ideation and behavior. The C-SSRS is an FDA-endorsed questionnaire administered by trained study personnel to screen for suicidality risk and ideation in patients participating in trials of CNS-active compounds. The Baseline/Screening Version of the C-SSRS, which assesses both lifetime history and history from the last 12 months, will be used at screening to determine subject eligibility. The Since Last Visit Version of the C-SSRS will be used at all subsequent visits specified.

Refer to [Section 6.1.4](#) for suicidality individual treatment-stopping criteria.

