5.2.3.6 Psychiatric Evaluations

The Columbia–Suicide Severity Rating Scale will be used during the study to monitor suicidal ideation and behavior. The Baseline/Screening Version of the C-SSRS, which assesses both lifetime history and history from the last 12 months, will be used at the Screening Visit to determine subject eligibility. The Since Last Visit Version of the C-SSRS will be used at all subsequent visits (Day 1, Week 4, Week 8, and Week 12) specified in [Table 7](#).

[figure not shown]

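### SAP 14.5 does not name the on-treatment C-SSRS form for listing, and tabulates 'Yes' answers by arm only if more than 5 subjects in a dose level give one

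*SAP*

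**What the plan says.** Both documents use two C-SSRS forms. The Baseline/Screening version is given once; Protocol 7.1.6.1 describes it as covering lifetime history and "history from the last 12 months, will be used at screening to determine subject eligibility". For everything after screening, SAP 5.2.3.6 states: "The Since Last Visit Version of the C-SSRS will be used at all subsequent visits", and names Day 1 and Weeks 4, 8 and 12.

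The reporting section, SAP 14.5, does three things:

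- It commits to a listing that begins "All responses from the Baseline/Screening Version of the" C-SSRS, and names no other version.
- It describes that form as covering lifetime history and "history from the last 6 months will be listed by subject and by visit".
- It says tables will include the ideation and behavior sections. It then makes the number and percentage of 'Yes' subjects, by treatment group and scheduled time point, conditional: they appear "if sufficient number (i.e., > 5 in any dose level) of subjects responded" 'Yes'.

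SAP 9.3.14.1 counts placebo, 50 mg, 100 mg and 200 mg as dose levels, so the condition can be met in any of the four.

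**The concern.** Protocol 6.1.4 treats tildacerfont as CNS-active and gives that as the reason for C-SSRS monitoring. The relevant safety output is therefore what subjects answered after the first dose, by arm. SAP 14.5 names for listing only the form completed before treatment, and makes the by-arm counts depend on a number of 'Yes' subjects that is large for arms of this size.

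At stake is a planned safety comparison built on data already collected. Other safety outputs carry no such condition: SAP 14.4 tabulates out-of-threshold ECG values by treatment and time point with no minimum count, and SAP 14.1 does the same for TEAEs by system organ class and preferred term.

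**Working it through.** **Arm sizes.** The plan gives no figure for the C-SSRS threshold, so the only figure to reproduce is the sample size behind the arms (Protocol 8.1, SAP 7). With difference 164, SD 154, two-sided alpha 0.05, 80% power and 2:1 allocation:

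- Placebo n = (1 + 1/2) × (1.96 + 0.8416)² × (154/164)² = 1.5 × 7.849 × 0.8818 = 10.4, rounded up to 11. Tildacerfont is 22, total 33.
- Dropout: 33 / 0.85 = 38.8, rounded up to 39, split 26 and 13.

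The stated 33 and 39 are reproduced. Power at 11/22 is 82.2% by the normal approximation and 79.8% by the noncentral t.

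**What the condition requires.** More than 5 means 6 or more: 6/26 = 23.1% of tildacerfont or 6/13 = 46.2% of placebo subjects.

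**Chance of meeting it in one dose level.** With a common 'Yes' probability p per subject in a period, P(X ≥ 6) = 1 − Σ (k = 0 to 5) C(n,k) p^k (1 − p)^(n−k). The documents give no p, so these rates are assumptions. SAP 15 says the study stopped early without giving the number enrolled, so n = 22 and n = 18 are assumed smaller sizes.

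| n in dose level | p = 5% | p = 10% | p = 15% | p = 20% | p for an even chance |
|---|---|---|---|---|---|
| 26 (planned tildacerfont) | 0.15% | 4.0% | 18.5% | 42% | 21.5% |
| 22 (assumed) | 0.06% | 1.8% | 10.0% | 26.7% | 25.4% |
| 18 (assumed) | 0.02% | 0.6% | 4.2% | 13.3% | 30.9% |
| 13 (planned placebo) | 0.002% | 0.09% | 0.75% | 3.0% | 42.5% |

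**Chance that any dose level meets it.** If three levels of 26 and placebo of 13 are treated as independent (an assumption), P(any) = 1 − (1 − a)³(1 − b), where a and b are the n = 26 and n = 13 entries. This gives 0.5% at p = 5%, 11.6% at 10% and 46% at 15%. At 20% it is 1 − (0.5775)³ × 0.970 = 81%. The same subjects pass through all three tildacerfont doses, and positive dependence between periods would lower these figures.

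**Chance that there is something to show.** P(at least one 'Yes' among 26) = 1 − (1 − p)^26, which is 40.9% at p = 2%, 73.6% at 5% and 93.5% at 10%. The matching chances that this dose level triggers the table are 0.001%, 0.15% and 4.0%.

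**Effect of counting by dose level.** Five different subjects answering 'Yes' at each of 50, 100 and 200 mg, against none on placebo, would be 15 of 26 tildacerfont subjects (58%) and would still not meet the condition.

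**Which answers reach other outputs.** Protocol 7.2.8 makes a 'Yes' to Questions 3-5 an AESI, and Protocol 6.1.4 does the same for suicidal behavior that is not an SAE. SAP 14.1 lists AESIs and tabulates TEAEs by treatment group. Questions 1-2 are outside the 7.2.8 definition, so they reach an AE output only if an investigator reports an AE. No section provides an item-by-visit C-SSRS comparison by arm other than the conditional one in 14.5.

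**The case against.** The strongest reply is that serious findings are not hidden. A reader might infer from 14.5 that on-treatment suicidality would almost never be reported by arm. The documents do not support that: Questions 3-5 events enter the AESI listing and the by-arm TEAE tables with no minimum count. An imbalance of four active to none on placebo in such events would be visible there.

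A reader might also infer that the condition conflicts with the study stopping rule in Protocol 6.1.9, "If 3 or more subjects on active drug experience a drug-related AESI", because 3 is fewer than 6. It does not. That rule counts drug-related AESIs of any type, on active drug only, and is applied during the study by an unblinded Medical Monitor. The 14.5 table is an end-of-study count of any 'Yes', regardless of relatedness. The two numbers measure different things.

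It can further be said that the listing sentence is a drafting slip. A form given only at screening cannot sensibly be listed by visit, and Protocol 8.3.5 commits to listing all safety data by subject. This is a fair reading and probably the intent. But SAP 4 gives the SAP precedence where the documents are inconsistent, so the text should say what is meant.

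Two points about the numbers also stand. The rates are assumed, and at 15-20% the table is no longer unlikely at the planned size. In addition, 14.5 counts a 'Yes' at any point without excluding screening or lifetime answers; if those count, the condition is easier to meet, but the resulting table would mix history with on-treatment answers.

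The recall-period mismatch is editorial: exclusion criterion 7a uses 6 months for ideation and 12 for behavior, and no on-treatment result depends on it. Finally, with few events a listing can be as informative as a sparse table. That holds only if the listing covers the on-treatment form.

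**Conclusion.** The concern holds in a limited form. As written, SAP 14.5 does not name the on-treatment C-SSRS form for listing, and a stated rule withholds the by-arm counts unless at least 6 subjects in one dose level answer 'Yes'. At the planned sizes, one tildacerfont dose level would trigger the table with probability 0.15% to 4.0% for assumed rates of 5% to 10%, and 18.5% to 42% for 15% to 20%. Each figure falls with the smaller enrolment after the early stop. The calculation assumes independent subjects with a common rate and counts only on-treatment answers.

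The loss is the item-level, on-treatment C-SSRS comparison by arm, above all Questions 1-2 and any answer not reported as an AE. Reporting of Questions 3-5 events through the AE outputs is intact, and there is no inconsistency with the study stopping rule.

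**What to change.** In SAP 14.5:

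1. List Baseline/Screening and Since Last Visit responses by subject and visit, naming both forms.
2. Delete the more-than-5 condition. Always tabulate 'Yes' answers given after the first dose, for each ideation and behavior item, by treatment group, dose level and visit.
3. Show screening and lifetime 'Yes' answers separately. Day 1 answers belong with the pre-treatment data, because clinic visits are in the early morning and study drug is taken in the evening (Protocol 3.1.2 and 5.1).
4. Reconcile the 6-month recall wording with the 12 months in SAP 5.2.3.6 and Protocol 7.1.6.1, according to the form actually used.

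The cost is a wording change, one listing and one small table from data already collected. The table may be sparse or all zeros. No protocol amendment or new assessment is needed.
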